Our initial hypothesis as reflected in the design of Stage 1 of the trial, is that a functional immune defect exists within the T lymphocyte compartment in recurrent/progressive glioblastoma patients. The neoadjuvant use of pembrolizumab (PD-1 blocking mAb) in this patient population will lead to a statistically significant increase in tumor infiltrating lymphocytes when compared to a concurrent control population. The combination of tumor tissue and optional imaging evaluations should provide insight into immune activation, antitumor effect and toxicity with immune checkpoint inhibitors.

An interim analysis of data from 35 enrolled patients from October 2016 to September 2017 in this trial has also shown that patients who were randomized to receive neoadjuvant pembrolizumab, with continued adjuvant therapy following surgery (Group A), had significantly extended overall survival compared to patients that were randomized to receive adjuvant, post-surgical PD-1 blockade alone (Group B) (hazard ratio = 0.39; P = 0.04, log-rank test). Neoadjuvant PD-1 blockade was associated with upregulation of T cell and interferon- γ -related genes, but

downregulation of cell cycle-related genes within the tumor, which was not seen in patients that received adjuvant therapy alone¹¹². Therefore, in a second stage extension of this trial (Stage 2), the specific effect of neoadjuvant pembrolizumab on the cell cycle and cancer proliferation related genetic signature within the tumor microenvironment of progressive/recurrent glioblastoma patients will be evaluated.

Specific procedures to be performed during the trial, as well as their prescribed times and associated visit windows, are outlined in the Study Calendar - Section 9.

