1.4 Exploratory Objectives

1.4.1 Objective: To evaluate the associations between exploratory biomarkers and clinical outcomes and adverse events these include:

- 1.4.1.1** Estimate correlation of quantitative assessments of TIL density or clonality with clinical responses to pembrolizumab in recurrent glioblastoma patients.
- 1.4.1.2** Estimate efficacy of pembrolizumab by PFS, second PFS and OS. (Groups A and B) as defined by RANO.
- 1.4.1.3** Estimate efficacy of pembrolizumab by PFS6, PFS, second PFS and OS. (Groups A and B) as defined by iRANO.
- 1.4.1.4** Explore effect of pembrolizumab on TIL proliferation (CD8+KI-67+ staining).
- 1.4.1.5** Estimate difference in PD-1 and PDL-1 IHC expression between Group A and B as well as between archived and study samples.
- 1.4.1.6** Explore whether oligoclonal T cell populations within tumor tissue are similarly expanded in peripheral blood after pembrolizumab, the magnitude of which correlates with clinical responses.
- 1.4.1.7** Explore if changes in specific MRI parameters correlate with tumor and peripheral blood immune responses.
- 1.4.1.8** Correlation of tumor mRNA from extracellular vesicles with outcome.

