5. TREATMENT PLAN

This is a pilot surgical trial to evaluate early immunologic pharmacodynamic parameters for the PD-1 checkpoint inhibitor, pembrolizumab (MK-3475), in patients with surgically accessible recurrent/progressive glioblastoma. The principle goal of this study is to understand, in surgically resectable recurrent/progressive GBM, if neoadjuvant pembrolizumab elicits a systemic immunologic response, a tumoral immunologic response and toxicity and if that response can be correlated with other non-invasive measures of pembrolizumab bioactivity (tumor, blood, imaging, and clinical outcomes). The study includes 2 stages, in the first stage (**Stage 1**), for optimal understanding of the effect of the drug on tumor tissue patients will be randomized in to Group A or Group B. In the second stage (**Stage 2**), additional patients will be enrolled to an expansion arm of Group A only to specifically study the effect of the drug on cell cycle/cancer proliferation related genetic signature.

Stage 1:

Groups A and B: Patients will be randomly assigned to either group A or B with a 1:1 randomization ratio prior to surgery. Patients in all groups will receive the study drug pembrolizumab after tumor resection. Only Group A will receive a single infusion of pembrolizumab of 200mg 14± 5 days prior to surgery (when scheduling, please keep in mind that the two pre-surgical plasma samples should be drawn greater than 10 days apart - see Table 6 for full details). Group B will not receive study drug prior to surgery. **This randomization scheme should not negatively impact study accrual and will provide an invaluable control cohort for PD evaluations.**

Group A: Neoadjuvant/adjuvant evaluation: Fifteen eligible patients will receive a single infusion of pembrolizumab of 200mg 14± 5 days prior to scheduled surgical resection for

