Group B: adjuvant evaluation: Fifteen eligible patients will not receive study drug prior to scheduled surgical resection for recurrent/progressive glioblastoma. The two required pre-surgical plasma samples should be drawn greater than 10 days apart - see Table 6 for full details). Tumor samples will be obtained at time of surgery. The tissue from this surgery (fresh, frozen and FFPE) and the archived tissue from the most recent surgery prior to registration revealing glioblastoma (FFPE) will be processed so as to best achieve the primary, secondary and exploratory PD objectives. After recovery from surgery (once participant has recovered from surgery, but no more than 35 days following surgery), patients will begin Q 3 week pembrolizumab at 200mg IV until tumor progression or adverse event requiring discontinuation of study drug. Blood samples will be obtained as pharmacodynamic markers throughout the study. Dose decreases and symptomatic management will occur based upon preset adverse event determination. DLTs will not be determined. The toxicity evaluation period will begin with registration and extend to 30 days after last treatment day. Patients will be followed for MRI changes, clinical exam and steroid doses from the registration period and extend to the second progression. After second progression, patients will be followed every 3 months for vital status until death.

Stage 2:

Group A expansion only: For this stage of the study, 25 additional patients will be enrolled to Group A only with a goal of 20 evaluable patients.

Expansion of Group A: Neoadjuvant/adjuvant evaluation: An additional 20-25 patients will receive a single infusion of pembrolizumab of 200mg 14± 5 days prior to scheduled surgical resection for recurrent/progressive glioblastoma (when scheduling, please keep in mind that the two pre-surgical plasma samples should be drawn greater than 10 days apart - see Table 6 for full details). Tumor samples will be obtained at time of surgery. The tissue from this surgery (fresh, frozen and FFPE) and the archived tissue from the archived tissue from the most recent surgery prior to registration revealing glioblastoma (FFPE) will be processed so as to best achieve the primary, secondary and exploratory PD objectives. After recovery from surgery (once participant has recovered from surgery, but no more than 35 days following surgery), patients will resume Q 3 week pembrolizumab at 200mg IV until tumor progression or adverse

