12.2.5 Analysis Population

12.2.5.1 Efficacy Analysis Populations

The Full Analysis Set (FAS) population will serve as the primary population for the analysis of efficacy data in this study. The FAS population consists of all subjects within each cohort who have received at least one dose of study treatment.

Two supportive analyses of the primary and selected secondary efficacy endpoints will be conducted. The first supportive analysis will be conducted in the FAS-2 population, defined as all subjects who meet the FAS population definition and have a post baseline scan OR discontinue the trial due to progressive disease/drug related AE. The second analysis will be conducted using the intention to treat (ITT) population, defined as all randomized subjects.

Subjects will be included in the cohort to which they are randomized for the analysis of efficacy data.

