12.2.6 Statistical Methods

Nominal p –values may be computed for efficacy analyses as a measure of strength of association between the endpoint and the treatment effect rather than formal tests of hypotheses. Unless otherwise stated, all statistical tests will be conducted at the $\alpha=0.05$ (2-sided) level.

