12.2.6.3 Statistical Methods for Exploratory Analyses

Variables involved in exploratory analyses will be examined graphically and summarized by descriptive statistics. Data transformation may be applied to quantitative variables prior to analyses if deemed necessary.

Bivariate association analyses will be conducted to evaluate the associations between exploratory biomarkers and clinical outcomes and adverse events for the objectives listed in 1.4. The analyses will be performed for each group separately and/or combined as deemed appropriate. Specifically, Pearson or Kendall's tau correlation coefficients will be calculated to evaluate the association between quantitative variables, Chi-squared tests or Fisher's exact tests will be used to examine the association between categorical or ordinal variables, and ANOVA will be performed to study the association between a quantitative variable and a categorical variable. The association between biomarkers and clinical outcomes (PFS and OS) will be evaluated using Cox regression. For markers with multiple measurements over time, data at a specific time point or change from pre-treatment will be used in the above bivariate analyses as deemed appropriate.

Changes in markers pre- and post-treatment will be assessed using paired t-tests.

Between-group comparisons will be conducted for PFS, OS, and PD-1, PDL-1 IHC expression. Survival analyses via Kaplan-Meier curves and log-rank tests will be used to estimate and compare PFS, second PFS, and OS between Group A and Group B. PD-1 and PDL-1 IHC expression will be compared between Groups A and B using two-sample t-tests.

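### The exploratory Group A v Group B survival tests are not limited to Stage 1, so on the natural reading non-randomised Stage 2 patients join Group A alone

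*Combined protocol and SAP*

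**What the plan says.** Section 12.2.6.3 plans Kaplan-Meier curves for the two groups and says that "log-rank tests will be used to estimate and compare PFS, second PFS, and OS between Group A and Group B". It names no stage, stratification or adjustment.

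In Stage 1 allocation is random: "Patients will be randomly assigned to either group A or B with a 1:1 randomization ratio prior to surgery". In Stage 2 it is not: "25 additional patients will be enrolled to Group A only with a goal of 20 evaluable patients". Section 5 describes Stage 2 as an expansion of Group A. Section 12.2.3 bases the Stage 2 gene-signature test on adding 20 patients to Group A and still calls Group B a concurrent control, although every Group B patient comes from Stage 1.

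Section 12.2.5.1 makes the FAS the primary efficacy set: "The FAS population consists of all subjects within each cohort who have received at least one dose of study treatment". The ITT set, all randomised subjects, is supportive only. The same section says that efficacy data are analysed by randomised cohort, which has no meaning for Stage 2 patients.

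Section 1.1 reports an interim OS result in favour of Group A from 35 patients enrolled from October 2016 to September 2017 ("hazard ratio = 0.39; P = 0.04, log-rank test") and then introduces Stage 2.

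On status, section 1.4 lists the objective as exploratory: "Estimate efficacy of pembrolizumab by PFS, second PFS and OS. (Groups A and B) as defined by RANO". Section 12.2.6 says that nominal efficacy P values may be computed "as a measure of strength of association between the endpoint and the treatment effect rather than formal tests of hypotheses", and sets a default two-sided level of 0.05.

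**The concern.** Stage 1 alone gives a randomised comparison of survival. If Stage 2 patients are pooled into Group A, they make up more than half of it: 20 of 35 (57%) with 15 Stage 1 patients and 20 added, or 25 of 40 (62.5%) with 25 added. They enrol later, with no counterpart in Group B. An unstratified log-rank test cannot separate a stage difference from a treatment difference, yet the result would look like the randomised comparison with a larger sample.

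The plan also leaves room for two analysts to report different OS comparisons, one on the FAS and one on the randomised patients, and both could claim to have followed it.

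A second matter applies to OS only. Stage 1 survival had already been compared, in Group A's favour, and the plan does not say that the final OS test includes those events.

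**Working it through.** **Plan's own figure.** The plan gives no events, sample size or power for the log-rank tests, so there is no design figure to reproduce. The interim result can be checked for plausibility. P = 0.04 two-sided gives z = 2.054, and |ln 0.39| = 0.942. Information is (2.054/0.942)² = 4.76, which at 1:1 means 4 × 4.76 = about 19 deaths. That is plausible for 35 patients.

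**Stage 2 holds no A v B information.** In a log-rank test stratified by stage, everyone at risk in Stage 2 is in Group A. Observed minus expected is therefore 0 at each Stage 2 event time, and so is its variance. Stage 2 can move the result only through the unstratified comparison with Stage 1 Group B.

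**Effect of pooling with no drug effect.** Simulated log-rank tests, two-sided 0.05. From the documents: 15 v 15 in Stage 1, 20 or 25 added to Group A, 18 months of Stage 2 accrual. Assumed: exponential survival, median OS 9 months, a 12-month gap between stages, 6 months of final follow-up; 18 v 17 was also run as a possible split of the 35 interim patients.

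| Stage 2 hazard relative to Stage 1 (assumed) | Pooled test, two-sided |
|---|---|
| 1.0 | 5.7-5.8% |
| 0.9 | 6.2-6.3% |
| 0.8 | 7.2-7.7% |
| 0.7 | 9.0-9.9% |
| 0.6 | 11.8-13.5% |

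The test restricted to Stage 1 gives 5.8-6.1% throughout; the excess over 5% is small-sample behaviour of the log-rank test. Other assumptions (median OS 10 months, 24 months of follow-up, 20 added) give pooled results favouring A in 3.4%, 7.0%, 10.1% and 14.2% of trials at hazards 1.0, 0.8, 0.7 and 0.6. Those rates count one direction only, so their nominal reference is 2.5%.

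**Carry-forward of the interim OS result.** If there is no difference in later events,

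P(final z > 1.96) = 1 − Φ[(1.96√I₂ − z₁√I₁)/√(I₂ − I₁)], with z₁√I₁ = 2.054 × √4.76 = 4.48.

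- Pooled, 35 v 15 (70:30), I₂ = D × 0.7 × 0.3. For an assumed D = 40, I₂ = 8.40: (5.68 − 4.48)/1.91 = 0.63, giving 26.5%. D = 45, 50 and 55 give 23.8%, 21.7% and 20.1%.
- Stage 1 only, 1:1, I₂ = D/4. For an assumed D = 30, I₂ = 7.50: (5.37 − 4.48)/1.66 = 0.54, giving about 30%. D = 33 gives about 27%.

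The formula treats later information as independent of the interim, which is only approximate for the pooled test. Simulation conditional on an interim z near 2.05 gives about 28% pooled with equal prognosis (17-36% over median OS of 6-15 months and interim follow-up of 1-8 months), and 28-32% for Stage 1 only. With a Stage 2 hazard of 0.9 to 0.7 the pooled figure rises to about 33-48%.

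**The case against.** The strongest reply is that nothing turns on these tests. They are exploratory, their P values are nominal, and the plan sets no pass rule. That stands, and it limits the weight of the point. It does not make a comparison that mixes stage with treatment interpretable as a measure of association between treatment and survival.

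A second reply is that the plan never says Stage 2 patients enter these tests, and that the ITT definition and the randomised-cohort rule do not fit them. This is right as far as it goes: pooling is inferred. But the FAS is primary, ITT is supportive, and the plan treats Stage 2 as more Group A patients. At best the text is ambiguous, and the same sentence would resolve it.

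A third reply is that the inflation depends on a prognosis shift whose size the documents do not give. This also stands. A worse Stage 2 case mix would bias against Group A instead.

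A reader might infer that a regimen with no benefit would pass far more often than the nominal 5%. The documents do not support that. Pooling without a shift adds nothing, and assumed hazards of 0.9 to 0.7 give about 6-10% in the main simulation. The 20-30% figures come from carrying forward the interim OS data, which a Stage 1-only test does equally, so they are no argument for the restriction. They do not extend to PFS or second PFS, for which no interim result is reported. Nor does section 1.1 say that Stage 2 was opened to confirm the OS finding; its stated aim is the cell-cycle signature.

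**Conclusion.** The point holds as one of bias and clarity in an exploratory analysis. On its natural reading, section 12.2.6.3 adds 20-25 later, non-randomised patients to one side of a comparison that Stage 1 can make on randomised patients alone. With no prognosis shift the error rate is unaffected (about 5.7% two-sided, against about 6%). With an assumed drug-unrelated Stage 2 hazard of 0.8, 0.7 or 0.6 it is roughly 7-8%, 9-11% or 12-14%. These figures rest on exponential survival and assumed follow-up, and the direction of any real shift is unknown.

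For OS only, given the interim result and no later difference, the chance of nominal significance for Group A is about 20-30% under the assumed event counts, pooled or not. Restricting to Stage 1 removes the stage bias but not this; only disclosure and a descriptive label deal with it. The change is worth making because it costs only wording, but no trial decision depends on it.

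**What to change.** In section 12.2.6.3:

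- Base the A v B log-rank tests and hazard ratios for PFS, second PFS and OS on patients randomised in Stage 1, analysed by assigned group.
- Report Stage 2 Group A separately, with its own Kaplan-Meier estimates and 95% confidence intervals, and no test against Stage 1 Group B.
- If a pooled Group A curve is shown, label it non-randomised and give it no P value.
- State that the OS comparison updates the interim look already reported in section 1.1 and is descriptive.

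This needs no new patients or data. The cost is precision: the comparison stays at about 30-35 patients, and its interval will be wider than a pooled analysis would appear to give.

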Activated Partial Thromboplastin Time (aPTT)	$\leq 1.5 \times$ institutional ULN unless subject is receiving anticoagulant therapy as long as PT or PTT is within therapeutic range of intended use of anticoagulants

^aCreatinine clearance should be calculated per institutional standard.

3.1.9 CT or MRI within 14 days prior of registration.

NOTE: Due to the fact that the screening MRI will not be used for response purposes, participants may be registered if screening CT or MRI is > 14 days of registration if prospective approval is received from Overall PI, [name] (for prospectively approved circumstances an eligibility exception will not need to be filed).

3.1.10 An interval of at least 4 weeks (to registration) between prior surgical resection or one week for stereotactic biopsy.

3.1.11 An interval of at least 12 weeks from the completion of radiation therapy to registration unless there is unequivocal histologic confirmation of tumor progression.

3.1.12 Participants must have recovered to grade 0 or 1 or pre-treatment baseline from clinically significant toxic effects of prior therapy (including but not limited to exceptions of alopecia, laboratory values listed per inclusion criteria, and lymphopenia which is common after therapy with temozolomide).

3.1.13 From registration, the following time periods must have elapsed: 5 half-lives from any investigational agent, 4 weeks from cytotoxic therapy (except 23 days for temozolomide and 6 weeks from nitrosoureas), 6 weeks from antibodies, or 4 weeks (or 5 half-lives, whichever is shorter) from other anti-tumor therapies (including vaccines). No wash-out period required from TTF.

3.1.14 Participants must have sufficient tissue from most recent surgery revealing glioblastoma or variants for submission following registration. The following amount of tissue is required:

- 1 formalin-fixed paraffin-embedded (FFPE) tumor tissue block

3.1.15 Patients with a prior or concurrent malignancy whose natural history or treatment does not have the potential to interfere with the safety or efficacy assessment of the trial are eligible.
NOTE: consultation with the Overall PI is highly recommended if enrollment of a patient with a prior or concurrent malignancy will be pursued.

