8. BIOMARKER STUDIES

The precise mechanism by which Pembrolizumab exerts anti-tumor activity is not clear but it is likely related to modulation of the immune system to generate anti-tumor immune responses that are capable of eliminating existing tumors and generating immune memory responses to prevent future relapse. The effect of PD-1 blockade on effector T cells and regulatory T cells is a critical component of anti-tumor activity. The current study will explore baseline levels as well as changes following pembrolizumab administration for association with outcome. In addition, archival tumor expression of PD-L1 will also be evaluated. Peripheral blood will be collected prior to initiation of study therapy, prior to surgery and periodically during the study. Archival tumor will also be collected on all patients. Since this is a surgery study, all tumor samples obtained during the study will be used to evaluate effect of therapy. In addition, if a biopsy or surgical resection is performed at the time of potential progression, a tumor sample (block or slides) should also be submitted if sufficient tumor material is available.

Evaluation of correlative immunologic biomarkers will be performed at the Brain Tumor Immunology Research Laboratory, UCLA Jonsson Comprehensive Cancer Center. Instructions for sample processing and shipping are provided in this section.

Please note that submitting institution is responsible for the costs of shipping and handling.

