8.3 IHC Measurements

A minimum of 1 formalin-fixed paraffin-embedded (FFPE) tumor tissue block from pre-study surgery confirming GBM are to be submitted within 60 days of registration. Additionally, a minimum 1 formalin-fixed paraffin-embedded (FFPE) tumor tissue block (preferred) or a minimum of 10 FFPE unstained sections from the protocol surgery are to be submitted per Table 6 below. Archival tumor samples from the protocol surgery should be shipped to the UCLA Brain Tumor Research Lab. Multi-plex IHC stained will be performed to assess: 1) the proportion of PD-L1 expression on GFAP+ tumor cells versus myeloid cells (CD68+ or CD163+) within the tumor microenvironment and subsequently batch shipped to a central lab determined by Merck for determination of PD-L1 expression at the end of the study.

NOTE: archival tumor tissue from pre-study surgery and protocol surgery submitted to the DFCI Coordinating Center outside of protocol mentioned timelines will not be logged as a violation. Sites will be tracked for compliance, but IRB reporting of out of window submission will not be required.

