TIL Density and TCR Overlap ([name]/[name]/[name], UCLA)	TCR ImmunoSeq and TCR Overlay (Adaptive Biotech.) on tumor tissue and peripheral blood mononuclear cell genomic DNA	Tumor (protocol surgery) and peripheral blood (Pre-Tx, Post-Tx)	200 mg of fresh tissue (approximately 20% tumor nuclei) sent in 2 mL Allprotect ® tissue reagent (Qiagen) or RNA-later® reagent Pre-treatment and post-treatment PBMC can be used from blood collected for flow cytometry (see below)	[name]. C/O [name] [name] [name] Los Angeles, CA 90095 [contact] Email: [contact] and [contact]
IHC measurements ([name]/[name]/[name], UCLA)	PD-1/PD-L1/CD8/CD4/CD8/Iba-1/CD68/GFAP IHC on FFPE tumor tissue	Archived and protocol surgery from tumor block	Archived: 1 formalin-fixed paraffin embedded (FFPE) tumor tissue block (preferred) from most recent surgery revealing glioblastoma Protocol Surgery: 1 FFPE tumor tissue block (preferred) or a minimum of 10 FFPE unstained sections	[name]. C/O [name] [name] [name] Los Angeles, CA 90095 [contact] Email: [contact] and [contact]
Peripheral blood T cell subsets/activation markers ([name]/[name]/[name], UCLA)	Flow Cytometry on peripheral blood mononuclear cells	Peripheral blood (Pre-surgery pre-treatment, pre-surgery post treatment, with every MRI)	Pre-surgery pre treatment blood (for Groups A and B) : 10 Green top tubes (10ml/tube – sodium heparin tubes preferred) following registration/randomization and pre-pembrolizumab for Group A Pre-surgery, day 7 post pembrolizumab administration (+/- 2 days): 10 Green top tubes 10-ml sodium heparin tubes preferred (should not be same timepoint as next 'pre-surgery post treatment' blood) Pre-surgery: 10 Green top tubes 10ml – sodium heparin tubes preferred (should be greater than 10 days from initial dose of Pembrolizumab for Group A – Group B should also have a sample drawn pre-surgery, greater than 10 days from initial sample)	[name]. C/O [name] [name] [name] Los Angeles, CA 90095 [contact] Email: [contact] and [contact]

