12.2.6.1 Statistical Methods for Primary Endpoint and Efficacy Analyses

Stage 1:

A two-sample Student's t-test will be used to test the difference of TIL density between the two groups. Data distribution will be examined prior to analysis. Data transformations will be performed as deemed appropriate.

Stage 2:

A two-sample Student's t-test will be used to test the difference of cell cycle-related signature between the two groups. Data distribution will be examined prior to analysis. Data transformations will be performed as deemed appropriate.

For PFS endpoint, the analyses will be conducted using pooled Group A and Group B patients. Kaplan-Meier (KM) curves and median estimates from the KM curves will be provided as appropriate. Percent PFS6 will be estimated from the KM curves and compared to historical controls. Subjects without efficacy evaluation data or without survival data will be censored at Day 1.

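### The exploratory Group A v Group B comparison of PD-1 and PD-L1 IHC could be adjusted for the archived value of the same marker: an optional gain in precision that depends on an unknown correlation

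*Combined protocol and SAP*

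**What the plan says.** The exploratory objective (Section 1.4, item 1.4.1.5) is to "Estimate difference in PD-1 and PDL-1 IHC expression between Group A and B as well as between archived and study samples". For the between-group part, Section 12.2.6.3 says "PD-1 and PDL-1 IHC expression will be compared between Groups A and B using two-sample t-tests". No covariate is named there, and no other section plans a baseline-adjusted A v B contrast of these markers. The same section plans paired t-tests for pre- to post-treatment change.

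The archived specimen is built into the trial:

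- Section 3.1, criterion 3.1.14: "Participants must have sufficient tissue from most recent surgery revealing glioblastoma or variants for submission following registration" (one FFPE block).
- Section 8: "Archival tumor will also be collected on all patients".
- Table 6 (Section 8.5) lists a single panel, "PD-1/PD-L1/CD8/CD4/CD8/Iba-1/CD68/GFAP IHC on FFPE tumor tissue", and gives the specimens as "Archived and protocol surgery from tumor block".
- Section 8.3 tolerates late blocks: archival tissue arriving "outside of protocol mentioned timelines will not be logged as a violation".

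TIL density, the Stage 1 primary endpoint, is also compared without adjustment (Section 12.2.6.1: "A two-sample Student's t-test will be used to test the difference of TIL density between the two groups"). Its source differs. Section 8.2 derives it by sequencing DNA from tumour taken at the protocol surgery and from blood, and no archived tumour is sequenced.

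**The concern.** Stage 1 plans 15 evaluable patients per group, and Section 5.5 rules out stratification. At that size, differences between patients in PD-1 or PD-L1 expression can be large relative to a group effect, and the groups can start apart by chance. The standard error of the baseline difference is sqrt(1/15 + 1/15) = 0.37 SD, so a gap of more than 0.5 SD in either direction arises about 17% of the time. The unadjusted t-test allows for this in its standard error but does nothing to reduce it.

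The archived block predates registration, so treatment cannot have affected it and it is a legitimate covariate. The planned paired tests do not do the same job. They address change within patients between two operations, over a period that may include other therapy, and not the randomised contrast. What is at stake is precision in an exploratory estimate. Validity is not in question.

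**Working it through.** **Inputs from the documents.** 15 + 15 evaluable patients in Stage 1; TIL difference 0.5, SD 0.5, one-sided alpha 0.05, stated power 85% (Section 12.2.3). The default test level, which governs the IHC comparison, is two-sided 0.05 (Section 12.2.6). Stage 2 adds about 20 evaluable patients to Group A only (Section 5).

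**Inputs assumed.** The correlation r between archived and protocol-surgery IHC is not given, so a range of 0 to 0.6 is used. No effect size or power is given for PD-1 or PD-L1.

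**Step 1: the plan's own figure.** The only Stage 1 power figure is for TIL density. A two-sample t-test with d = 0.5/0.5 = 1, 15 + 15 and one-sided 0.05 has 84.8% power by the noncentral t, which agrees with the stated 85%. This checks the method only; it says nothing about IHC.

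**Step 2: variance of the adjusted contrast.** Given the covariate, the ANCOVA variance is s²(1 - r²)(1/n1 + 1/n2)(1 + T²/(N - 2)), where T is the t statistic for the baseline difference. Under randomisation with a normal covariate, E[T²] = (N - 2)/(N - 4). The expected ratio to the t-test variance is therefore

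(1 - r²)(1 + 1/(N - 4)) = (1 - r²)(N - 3)/(N - 4).

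At N = 30 this is (1 - r²) × 27/26.

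**Step 3: results at 15 v 15.** The power column uses d = 1.06, at which the two-sided t-test has 80% power. It comes from the noncentral t on 27 df, averaged over chance baseline imbalance.

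| Assumed r | Variance ratio | Change | ANCOVA power (t-test 80%) |
|---|---|---|---|
| 0 | 1.038 | +4% | 78.4% |
| 0.2 | 0.997 | about 0% | 80.0% |
| 0.3 | 0.945 | -5.5% | 82.1% |
| 0.5 | 0.779 | -22% | 88.7% |
| 0.6 | 0.665 | -34% | 92.9% |

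**Step 4: break-even.** (1 - r²) × 27/26 = 1 gives r² = 1/27, so |r| = 0.19. The largest loss is at r = 0: 4% in variance, or 80 - 78.4 = 1.6 points of power.

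**Step 5: why not change scores.** A t-test on protocol-surgery minus archived values has variance ratio 2(1 - r), taking equal SDs. That is 1.4 at r = 0.3 and 1.0 at r = 0.5, so it loses precision unless r exceeds 0.5.

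**Step 6: if Stage 2 patients are included.** With 35 v 15 the ratio is (1 - r²) × 47/46: 1.022, 0.930 and 0.766 at r = 0, 0.3 and 0.5, with break-even at sqrt(1/47) = 0.15. The derivation in Step 2 relies on randomisation, which does not cover the added Group A patients.

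**The case against.** The strongest reply is that nothing here is wrong. Under Stage 1 randomisation the t-test is valid, and its standard error already reflects chance imbalance. The objective is exploratory, no decision hangs on it, and the introduction to Section 12 lets exploratory analyses change provided the clinical study report explains when and why. All of that stands, and it sets the severity.

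The second reply is that the covariate may be weak. The archived block comes from the most recent surgery before registration, which may predate radiotherapy (prior radiotherapy is required by 3.1.5) or other treatment. A low r is plausible, and below about 0.19 the adjustment costs a little. This also stands. The answer is that the loss is capped at about 4% in variance, while a moderate correlation gains several times that.

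Three stronger readings are tempting, and the documents do not support them:

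- A reader might infer that a free gain is being discarded. It is free of new samples and assays, but the gain is conditional on r. Universal availability of the block is a plan, not a guarantee, since late blocks are tolerated.
- A reader might infer that the archived data go unused. They do not: archived v study contrasts are an objective, and paired tests of pre- to post-treatment change are planned.
- A reader might infer that the primary TIL test ignores each patient's own baseline. No archived TIL density exists. Archived CD8 IHC is a different assay on an older specimen, and nothing in the documents supports a particular correlation between the two, so power gains should not be quoted for TIL density.

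**Conclusion.** The point holds for the exploratory PD-1 and PD-L1 IHC comparison only. A baseline measurement of the same marker is planned for every patient, and the A v B test does not use it. The variance effect at 15 v 15 ranges from +4% to -34% over assumed r of 0 to 0.6. These figures rest on an assumed correlation, a roughly linear relation, a normally distributed covariate and the planned group sizes. The practical gain for PD-1 and PD-L1 cannot be stated more closely, because the plan gives neither an effect size nor a correlation.

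The randomisation argument covers Stage 1. Section 12.2.6.3 does not say whether Stage 2 Group A patients enter the comparison. If they do, adjustment may reduce imbalance but cannot restore randomisation. This is an optional improvement to an exploratory analysis.

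**What to change.** In Section 12.2.6.3, replace the between-group t-tests for PD-1 and PD-L1 with the following:

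- **Main analysis:** ANCOVA of the protocol-surgery value on group, with the archived value of the same marker, scored the same way, as covariate, in the randomised Stage 1 patients. Use rank ANCOVA or a transformation if the values are skewed; the section already allows transformation.
- **Sensitivity analysis:** the unadjusted two-sample t-test.
- **Missing archived values:** impute the overall covariate mean, pooled over both groups, so that no patient is dropped.
- **Stage 2 patients:** if they are added, report that comparison separately and label it as not randomised.

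An analysis of TIL density adjusted for archived CD8 IHC may be listed as optional and supportive. The primary TIL test stays as it is.

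The cost is a few lines of SAP text and one degree of freedom, with no new sample or assay. Because Section 1.1 reports interim A v B results from 35 enrolled patients, the text should record when the adjusted analysis was added and not present it as predating those data. Section 12 requires a protocol amendment for changes to primary or key secondary hypotheses or their methods; for an exploratory analysis, an explanation in the clinical study report is enough.
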